### **8.7.4. Physical Examination and Medical History**

Physical examination data will be summarized using frequencies for each visit, Body System, and result by baseline, day 1, end of cycle 4, day 1 of each additional cycle and day 1 of cycle 9 or end of treatment for the safety population. The incidence of abnormalities at each visit for each Body System will be

summarized by frequency counts. A by-patient listing of all physical examination data will be displayed. Unscheduled visits will only be displayed in the listings.

Medical history data will be presented with a by-patient listing.

#### **8.7.5. Electrocardiogram data**

A by-patient listing of all ECG data at pre-study will be displayed.

#### **8.7.6. Clinical Laboratory Data**

Numeric clinical laboratory data will be summarized using descriptive statistics. Non-numeric laboratory tests will be summarized separately using frequency counts on unique responses. Individual change from baseline in lab values will be calculated and summarized descriptively. The incidence of treatment-emergent graded abnormalities (shown as High, Low, or Abnormal depending on the test) at each visit for each laboratory test will be summarized by frequency counts. Listings of abnormal laboratory results will be produced, showing normal ranges, out-of-range flags, and toxicity grades.

All clinical laboratory data with normal ranges, out-of-range flags, and toxicity grades will be listed by patient. Unscheduled visits will only be displayed in the listings.

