3.0 Patient Eligibility

3.1 Eligibility Criteria

NOTE: Phase I Only – Prior to discussing protocol entry with the patients **AND** prior to registering in the electronic data capture (eDC) system, call the PrECOG Project Manager to ensure that a place on the protocol is open to the patient. The Project Manager contact information is located in the Study Reference Manual.

3.11 ≥ 18 years of age.

3.12 Diagnosed with previously treated multiple myeloma (please see Appendix II for definition of myeloma).

3.13 Patients must have measurable disease assessed by one of the following ≤ 21 days prior to registration:

- Serum monoclonal protein ≥ 1 g by protein electrophoresis*
- >200 mg of monoclonal protein in the urine on 24 hour electrophoresis*
- Serum immunoglobulin free light chain ≥ 10 mg/dL **AND** abnormal serum immunoglobulin kappa to lambda free light chain ratio
- Monoclonal bone marrow plasmacytosis $\geq 30\%$ (evaluable disease)

*NOTE: If both serum and urine m-components are present, both must be followed in order to evaluate response.

3.14 All previous cancer therapy including chemotherapy, radiation, hormonal therapy and surgery, must have been discontinued ≥ 2 weeks prior to registration.

3.15 ECOG Performance Status (PS) 0, 1, or 2 (see Appendix III).

3.16 Acceptable organ and marrow function ≤ 21 days prior to registration as defined below:

- Absolute neutrophil count ≥ 1000 cells/mm³
- Platelet count $\geq 75,000$ cells/mm³
- Total bilirubin ≤ 2 mg/dL.
- AST (SGOT) and ALT (SGPT) $\leq 3 \times$ ULN

3.17 Renal impairment at baseline as measured by serum creatinine clearance (CrCl) ≤ 60 mL/min ≤ 21 days prior to registration (see Appendix IV).

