16.22 Toxicity Profile

As per NCI CTCAE V4.0, the term “toxicity” is defined as adverse events that are classified as either possibly, probably, or definitely related to study treatment. Non-hematologic toxicities will be evaluated via the ordinal CTCAE standard toxicity grading. Hematologic toxicity measures of thrombocytopenia, neutropenia, and leukopenia will be

assessed using continuous variables as the outcome measures (primarily nadir) as well as categorization via CTCAE standard toxicity grading.

Overall toxicity incidence as well as toxicity profiles by dose level will be explored and summarized. Frequency distributions, graphical techniques and other descriptive measures will form the basis of these analyses.

Further, the overall toxicity profiles and the MTD will be compared in an exploratory fashion among the three groups for any possible differences.

Lastly, the duration of treatment, dose level and total dose per agent each cycle will be summarized using descriptive statistics overall per group and by dose level per group.

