### **8.7.3. Adverse Events**

Adverse events will be assessed in the safety population.

TEAEs are those that occur after administration of the first study dose until completion of the follow up evaluations. In the case where the start date of the AE is unknown, it will be assumed to be treatment-emergent. Treatment-emergent AEs (TEAEs) will be summarized by system-organ-class (SOC) and preferred term (PT) using the Medical Dictionary for Regulatory Activities (MedDRA®). The frequency of patients who experience TEAEs will be summarized overall cycle. Patients, having the same AE more than once per group, will be counted once for each PT and once within each SOC.

All AEs are listed by patient, including non-treatment-emergent (i.e., pre-dosing or post-dosing) AEs, if applicable. Separate patient data listings are provided for patients who experience treatment-emergent SAEs, TEAEs leading to early termination from the study, or fatal TEAEs.

Additional summary tables will display the number of patients with treatment-emergent AEs by maximum intensity, treatment-emergent AEs by strongest relationship to study drug, and treatment-emergent AEs that led to premature discontinuation of study classified by renal impairment group, system organ class and preferred term. The total number of all treatment-emergent AEs, serious TEAEs, TEAEs by maximum severity, treatment-related TEAEs, TEAEs leading to discontinuations, and TEAEs leading to death will also be summarized by renal impairment group.

CTC Version 4.0 will be used.

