### **9. SUMMARY OF CHANGES FROM PROTOCOL-SPECIFIED ANALYSES**

No changes are planned.

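### SAP 8.7.6 tabulates graded laboratory abnormalities only as High, Low or Abnormal and leaves treatment-emergent undefined for values abnormal at baseline, so its incidence table cannot show worsening by grade

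*SAP*

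**What the plan says.** SAP 8.7.6 plans four kinds of laboratory output:

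- descriptive statistics of numeric values;
- change from baseline: "Individual change from baseline in lab values will be calculated and summarized descriptively";
- a frequency table of abnormalities: "The incidence of treatment-emergent graded abnormalities (shown as High, Low, or Abnormal depending on the test) at each visit for each laboratory test";
- listings: "All clinical laboratory data with normal ranges, out-of-range flags, and toxicity grades will be listed by patient".

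It adds: "Unscheduled visits will only be displayed in the listings". Toxicity grades are named only for the listings. The SAP text mentions no shift table and no table of worst post-baseline grade. The table shells are in a separate document that was not available.

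The SAP defines treatment-emergent only for adverse events, by timing (8.7.3): "TEAEs are those that occur after administration of the first study dose until completion of the follow up evaluations".

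Protocol 16.22, within the phase I analysis plan, says that thrombocytopenia, neutropenia and leukopenia are to be "assessed using continuous variables as the outcome measures (primarily nadir) as well as categorization via CTCAE standard toxicity grading". SAP 9, on changes from the protocol's analyses, reads: "No changes are planned".

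**The concern.** The incidence table is where a reader of the study report would look for the rate of laboratory toxicity in each renal group. Its title promises graded abnormalities, but its columns show only whether a value is out of range. That loss is tolerable where most patients start with normal values. Here entry requires impaired renal function (Protocol 3.17) and permits an absolute neutrophil count (ANC) down to 1,000 and platelets down to 75,000 cells/mm³ (Protocol 3.16). In such patients the informative event is often a move from abnormal to more abnormal, and an out-of-range flag does not register that.

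Two things are at stake. Kidney failure is among the serious risks in Protocol 15.16, and renal function over time is secondary objective 2.23. The protocol's background also reports hematologic toxicity as Grade 3-4 rates by renal function (Protocol 1.3: thrombocytopenia 13.8% below CrCl 50 mL/min, 18.8% below 30). A High/Low table cannot yield a rate in that form.

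**Working it through.** The plan states no figure to reproduce. The check sets the sections side by side and adds short arithmetic on baseline creatinine.

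**1. Three possible meanings of treatment-emergent for a laboratory value.** Take a patient who enters with platelets at the floor of 75,000 and falls to 49,000. The change is 49,000 − 75,000 = −26,000, and Protocol Table 8.31 puts counts below 50,000 at Grade 3 or worse. Assume that the laboratory's lower limit of normal is above 75,000 (the documents give none). The flag is then Low at both times.

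| Rule | This patient | Patient with High creatinine at entry that rises further | Mild and Grade 4 distinguished? |
|---|---|---|---|
| Newly flagged after dosing | not counted | not counted | no |
| Any abnormal value after first dose (the AE rule) | counted as Low, as without the fall | counted as High, as without the rise | no |
| Grade above baseline grade | counted as Low | counted as High if the grade rises | no |

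The third rule counts the right patients but still hides severity. No reading gives a Grade 3-4 rate.

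**2. How many patients start with High creatinine?** Inverting the Cockcroft-Gault formula in Protocol Appendix IV:

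creatinine = (140 − age) × weight × (0.85 if female) / (72 × CrCl).

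At CrCl 30 the denominator is 72 × 30 = 2,160. For assumed ages 55-80 and weights 55-80 kg:

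- woman, 80 y, 55 kg: 60 × 55 × 0.85 / 2,160 = 1.30 mg/dL (lowest);
- man, 70 y, 75 kg: 70 × 75 / 2,160 = 2.43 mg/dL;
- man, 55 y, 80 kg: 85 × 80 / 2,160 = 3.15 mg/dL (highest).

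Groups B and C lie below CrCl 30, so at a given age, sex and weight their formula values are higher still. With an assumed upper limit of normal of 1.2-1.3 mg/dL, nearly all would be High at entry.

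At CrCl 60 the values halve, to about 0.65-1.57 mg/dL, so part of Group A starts within range. The protocol's substitution rule does not change that: the 80-year-old woman with a measured 0.65 is entered as 1, giving 60 × 55 × 0.85 / 72 = 39 mL/min, which is still Group A.

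**3. Where worsening could be seen instead.**

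- Change from baseline enters descriptive summaries. SAP 8.2 includes minimum and maximum and presents tables by renal group.
- SAP 8.7.3 tabulates adverse events by maximum intensity and renal group. Protocol 10.2 names hemoglobin, neutrophils and platelets for collection at baseline and each evaluation.
- Creatinine and leukocytes are not in the 10.2 table. They reach the adverse-event tables only if reported under 10.21, which takes Grade 3-4 events whatever the attribution but Grade 1-2 events only when judged at least possibly related.

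**4. Which draws feed the tables.** SAP 6.4 names screening, Day 1 of cycles 1-4, end of cycle 4, Day 1 of later cycles, and cycle 9 or end of treatment. Protocol 4.0 also draws blood counts and serum creatinine on Days 8, 15 and 22 of the first four cycles. Protocol 8.21 requires ANC of at least 1,000 and platelets of at least 50,000 per µL to start a cycle. A table built on the SAP 6.4 visits would therefore favor recovered counts and could miss nadirs. SAP 8.7 also takes the first of any repeated post-dose values at a visit, and 8.7.6 sends unscheduled results to listings only.

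**5. Protocol against SAP.** Protocol 16.22 plans nadirs and CTCAE-grade categories for three cytopenias. SAP 8.7.6 names neither as a summary. SAP 2.1 says that the SAP supersedes the protocol's statistical considerations and that substantial differences will be identified. SAP 9 identifies none.

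**The case against.** The best reply is that little is actually lost. The section that holds the table also summarizes change from baseline and lists every graded value. A large platelet fall at a scheduled visit would show as a visit minimum and as a large change. Graded cytopenias should reach the maximum-intensity tables by renal group because Protocol 10.2 specifies them. Protocol 16.22 is a phase I plan, described in 16.2 as exploratory, and does not cover creatinine. For renal function, Protocol 16.37 asks only for descriptive statistics, which 8.7.6 supplies. The shells may already contain a shift table.

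Most of this stands, and it limits the point. It rules out three stronger readings that a reader might infer:

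- **That severe worsening appears nowhere.** It can be found in the summaries, listings and adverse-event tables just named.
- **That the treatment-emergent High-creatinine rate would be near zero.** That presumes a newly-flagged rule which the SAP does not state. Its only definition, by timing, would push the rate toward 100% in Groups B and C.
- **That a definite number of severe thrombocytopenia cases would be missed.** The 18.8% comes from 16 patients (3/16 = 18.75%), and the documents give no share of patients starting with low platelets. Low counts are permitted at entry, not required.

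The other outputs still do not replace a graded table. Averages dilute a few severe cases, and a visit minimum describes one patient. Listings give no rates. The adverse-event tables do not compare with baseline grade, and for creatinine they depend on reporting.

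**Conclusion.** The point holds as a gap in the SAP text. The laboratory incidence table is called graded but shows no grades, and its key term is undefined for values abnormal at entry. Whichever meaning is chosen, it cannot show worsening by grade or separate mild from severe. The gap matters most for creatinine in Groups B and C, where most patients probably start out of range and the adverse-event route is not assured; Group A is less affected. The missing 16.22 summaries are a second, undeclared difference from the protocol.

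The size is modest. This is descriptive safety output; the primary endpoint, the maximum tolerated dose and the stopping rule are untouched. No count of hidden events can be supported. The conclusion rests on assumed laboratory limits (creatinine upper limit 1.2-1.3 mg/dL, platelet lower limit above 75,000), on illustrative ages and weights, and on the unseen shells not already supplying these tables. The lack of grades in the planned display needs none of the laboratory-limit or patient-profile assumptions.

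**What to change.** Amend SAP 8.7.6 as follows:

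1. Tabulate abnormalities by CTCAE v4.0 grade, with direction shown where a test can be graded both ways. Keep High/Low/Abnormal flags only for tests without a CTCAE grade.
2. Define a treatment-emergent laboratory abnormality as a post-dose grade above the baseline grade.
3. Add a shift table of baseline grade against worst post-baseline grade, by renal group, for hemoglobin, ANC, WBC, platelets and creatinine. Use all post-dose values, including Days 8, 15 and 22 and unscheduled draws, and state that this table is an exception to the first-value rule in 8.7 and the listings-only rule in 8.7.6.
4. Restore the nadir summary of Protocol 16.22, or record its omission in SAP 9.

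The cost is SAP wording and one or two extra shells. Grades are already planned for the listings, so no new data are needed. If the shells already include such tables, only the wording has to be brought into line.

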4.0 Test Schedule

*Treatment should begin \leq 7 working days from registration
 *Variations of +/- 3 days of the scheduled visits are permitted

	\leq21 days prior to registration	Cycle 1 only	For Each of the First Four Cycles				End of Cycle 4	Day 1 Each additional cycle ¹⁷	Day 1 of cycle 9 or at end of treatment	Follow-Up ^{16,18}
			Day 6	Day 1	Day 8	Day 15				
History & Exam, Wt., PS Assessment	X		X ¹²				X	X	X	
Height	X									
CBC w/differential	X		X ¹³	X	X	X		X ¹³		
Chemistry Panel (Na,K,Ca,AST,ALT,Alk Phos,Total Bili, Glucose, Creatinine, Albumin)	X		X	X ¹⁴	X ¹⁴	X ¹⁴	X	X	X	
Serum Creatinine Clearance ¹	X		X				X	X	X	
LDH, Beta-2 Microglobulin, C-Reactive Protein	X						X		X	
Serum TSH ²	X		X					X		
SPEP ³	X		X ¹²				X	X	X	
UPEP (24hr collection) ³	X		X ¹²				X	X	X	
Quantitative Immunoglobulins ³	X		X ¹²				X	X	X	
Serum Free Light Chains ³	X		X ¹²				X	X	X	
Immunofixation-Serum & Urine ⁴	X						X		X	
Bone Marrow Biopsy w/aspirate	X ⁵						X ¹⁵		X ¹⁵	X ¹⁹
Bone Marrow-FISH, cytogenetics	X ⁵									
Metastatic Bone Survey w/ long bones	X ⁵						X		X	
Chest X-Ray	X									

	≤21 days prior to registration	Cycle 1 only	For Each of the First Four Cycles					End of Cycle 4	Day 1 Each additional cycle¹⁷	Day 1 of cycle 9 or at end of treatment	Follow-Up^{16,18}
			Day 6	Day 1	Day 8	Day 15	Day 22				
ECG	X										
Pharmacokinetics ^{6, R}		X ⁶									
INR ⁷			X ⁷	X ⁷	X ⁷	X ⁷	X ⁷	X ⁷	X ⁷	X ⁷	
Pregnancy Testing ⁸	X ⁸		X ⁸						X ⁸	X ⁸	
Education and Counseling Guidance Document ⁹			X ⁹						X ⁹	X ⁹	
Dispense Study Drug ¹⁰			X ¹⁰						X ¹⁰		
Study Drug Compliance (Medication Diary)			X						X	X	
Adverse Event Assessment ¹¹				X	X	X	X ¹⁶	X	X ¹⁶	X ¹⁶	
Survival and Malignancy Surveillance											X ¹⁸

1. Creatinine clearance will be estimated using the Cockcroft-Gault formula. If the patient is >65 y/o and creatinine is <1, use 1 as serum creatinine value to calculate the creatinine clearance, see Appendix IV.
2. To be completed at baseline and then every 3 months.
3. Required at baseline, and then only required if used to assess disease response (see Section 11.2, Table 11.2).
4. Is required at study entry only if not previously performed or test results not available. If complete response is seen a 2nd immunofixation should be performed 4 weeks later to confirm. Urine immunofixation is only required if positive at study entry.

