9. All patients must be counseled about pregnancy precautions, risks of fetal exposure and other risks. The counseling must be done on Day 1 of each cycle (or at a minimum of every 28 days) throughout the entire duration of lenalidomide treatment, including dose interruptions, and at lenalidomide discontinuation. The Appendix VI: Education and Counseling Guidance Document must be completed by a trained Counselor (Counselors will be trained by Celgene).
10. Only enough lenalidomide for 1 cycle of therapy may be provided to the patient each cycle.
11. Refer to Section 10.2 for minimum events to be collected at baseline and each evaluation.
12. Except Day 1 of Cycle 1.
13. On Day 1 of each cycle, the ANC must be $\geq 1,000/\mu\text{L}$ and the platelet count must be $\geq 50,000/\mu\text{L}$.
14. Serum creatinine only.
15. Bone marrow aspirate and biopsy are **only** required to document or confirm CR or sCR, except for patients with evaluable disease **only**, where a bone marrow is required to document all response categories including progression (see Section 11.3). However, a second confirmatory bone marrow is **not** required to confirm response.
16. An additional safety assessment will be done 30 days (+/- 2 days) following the last dose of study drug.
17. Therapy may be interrupted to allow for stem cell harvest and mobilization for patients treated beyond 4 cycles.
18. Follow-up every 6 months for survival, second primary malignancy diagnosis, and recurrence of any prior malignancy (if applicable) x 3 years. If patient has not progressed at off-study, document date of progression. This should include subjects who may have discontinued the study at any time or for any reason, who may be in a survival follow-up period, or who may have died. Following this 3 year time period, reporting of all identified cases of subsequently diagnosed second primary malignancies is voluntary by the treating physician to the manufacturer.
19. Note: In addition to the standard evaluation for prolonged cytopenias that do not recover after discontinuation of treatment, a bone marrow exam should be considered, in patients with the following parameters: no leukopenia at the time of multiple myeloma diagnosis, no active multiple myeloma at the time of the cytopenia, no vitamin or element deficiency to explain the cause of the cytopenia(s).

R Research test. Will be charged to study and not to patient's account.

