16.23 Timed Endpoints

The data on time-related variables will be summarized descriptively. These include time until any treatment related toxicity, time until treatment related grade 3+ toxicity, time until hematologic nadirs (WBC, ANC, platelets), time to progression and time to treatment failure, where time to treatment failure is defined as the time from registration to documentation of progression, unacceptable toxicity, or refusal to continue participation by the patient.

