## **6.4. Clinical Laboratory Assessments**

Clinical laboratory tests will be collected at screening, day 1 of cycles 1 through 4, end of cycle 4, day 1 of each additional cycle and day 1 of cycle 9 or end of treatment.

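### The SAP text carries no blood-count nadir or time-to-nadir summary, though the protocol's exploratory Phase I plan specifies both, and its laboratory visit list and unscheduled-visit rule would not supply one

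*SAP*

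**What the plan says.** **Protocol.** Section 16.22, within the Phase I analysis plan, says the three cytopenias are to be "assessed using continuous variables as the outcome measures (primarily nadir) as well as categorization via CTCAE standard toxicity grading". It also asks for toxicity profiles by dose level. Section 16.23 includes "time until hematologic nadirs (WBC, ANC, platelets" among the time-related variables. In the Section 4.0 test schedule, the row "CBC w/differential" is marked at screening, on Days 1, 8, 15 and 22 of each of the first four cycles, and on Day 1 of later cycles.

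**SAP.** Section 6.4 states: "Clinical laboratory tests will be collected at screening, day 1 of cycles 1 through 4, end of cycle 4", followed by Day 1 of later cycles and Cycle 9 or end of treatment. Section 8.7.6 summarises values, changes from baseline and abnormality counts by visit, shows the abnormalities as high, low or abnormal, and adds: "Unscheduled visits will only be displayed in the listings". The time-to-event endpoints in 8.4.2 are survival, progression-free survival, duration of response and time to treatment failure. Section 2.1 gives the SAP precedence over the protocol's statistics and promises to identify substantial differences. Section 9 reads: "No changes are planned".

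**The concern.** A measure that the protocol names has no counterpart in the document that replaces the protocol's statistics, and the omission is not declared.

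The remaining rules do not rebuild it. A by-visit mean or frequency is not a per-patient minimum, even when every visit is included. If the 6.4 list is taken as the set of tabulated visits, the mid-cycle counts drop out as well.

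Marrow suppression is central to this trial. Protocol 1.3 reports falling neutrophil and platelet counts as the dose-limiting toxicities of lenalidomide. It also cites grade 3-4 thrombocytopenia of 18.8% below and 5.5% above a creatinine clearance of 30 mL/min. A description of how far counts fall, by renal group and dose level, is what a reader would look for. Laboratory tables weighted toward cycle-start counts may give a milder picture.

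**Working it through.** The plan states no figure for this point, so there is none to reproduce. The check compares the two schedules and then follows the SAP's rules.

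**1. Scheduled blood counts, Cycles 1 to 4**

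| | Protocol 4.0 | In SAP 6.4 list | Not in list |
|---|---|---|---|
| All | 4 days × 4 cycles = 16 | Day 1 × 4 = 4 | 16 − 4 = 12 (12/16 = 75%) |
| After first dose (Cycle 1 Day 1 taken as pre-dose) | 16 − 1 = 15 | 4 − 1 = 3 | 15 − 3 = 12 (12/15 = 80%) |
| Cycle 1, after first dose | Days 8, 15, 22 = 3 | 0 | 3 of 3 |

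SAP 6.4 also lists the end of Cycle 4, but the protocol's blood-count row has no mark in that column, so it adds no scheduled count. Cycle 1 is the window for dose-limiting toxicity (Protocol 7.22).

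**2. Off-schedule counts.** Protocol 8.21 requires weekly counts while a cycle start is held. These fall between planned visits, so SAP 8.7.6 would put them in listings only. Table 8.31 also requires weekly counts during mid-cycle holds. In Cycles 1 to 4 those can coincide with the scheduled Days 8, 15 and 22. From Cycle 5 only Day 1 is scheduled, so mid-cycle counts are off schedule.

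**3. What Day 1 counts can show.** The test-schedule footnote begins "On Day 1 of each cycle, the ANC must be" and sets at least 1,000/µL, with platelets at least 50,000/µL. Protocol 8.21 holds the cycle otherwise. Table 8.31 equates platelets below 50,000/mm³ with grade 3 or worse. A Day 1 count on which treatment actually starts therefore cannot show grade 3 thrombocytopenia or an ANC below 1,000. A Day 1 count that fails the requirement can still be tabulated, because SAP 8.7 uses the first of any repeated post-dose measurements at a visit.

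**4. Search of the SAP for an equivalent**

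| Protocol item | In the SAP text |
|---|---|
| Nadir of counts (16.22) | None |
| Time to nadir (16.23) | None |
| CTCAE grade of cytopenia (16.22) | Highest intensity per event in the adverse event tables (8.7.3); laboratory grades in listings (8.7.6) |
| By dose level (16.22) | Tables by renal group (8.2) |

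**5. Size of the understatement.** The documents give no course of counts over a cycle, so the distance between true nadirs and tabulated values cannot be computed. The visit counts above are what can be stated.

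**The case against.** The case for leaving the SAP alone is substantial.

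- **Worst grade is largely covered.** SAP 8.7.3 tabulates treatment-emergent events by maximum intensity and renal group. Protocol 10.2 requires neutrophils and platelets to be graded at each evaluation, and the adverse event row of the test schedule includes Days 8, 15 and 22. White cells are not in that solicited table, though 10.21 still collects grade 3-4 events and related grade 1-2 events. This stands. A reader might infer that worst cytopenia would go untabulated; the documents do not support that. What these tables lack is the continuous nadir, its timing and the split by dose level.
- **SAP 8.7.6 does not restrict its tables to Day 1.** It speaks of each visit. The list is in 6.4, a description of data collection, and Days 8, 15 and 22 are scheduled visits, so the unscheduled-visit rule does not reach them. This stands in part: their exclusion is a plausible reading of 6.4, not an explicit rule. Even if they are tabulated, no per-patient minimum is derived.
- **Low Day 1 counts are possible.** It is tempting to say that Day 1 tables show only recovered counts. The first-measurement rule contradicts that.
- **Not every count during a hold is unscheduled.** Step 2 of the working shows the overlap in Cycles 1 to 4, and the SAP does not define the term.
- **Little rests on the measure.** Section 16.2 calls the Phase I results exploratory. MTD decisions use the event definitions in 7.22 and 7.23, the stopping rule in 16.4 uses non-hematologic events, and the Phase II safety analysis in 16.37 asks for maximum grade. This stands and limits the importance.
- **The table templates are a separate document.** They may contain a nadir table. That cannot be excluded, but the SAP text would still give no derivation rule.

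**Conclusion.** The point holds as an undeclared gap between protocol and SAP in an exploratory Phase I safety measure. Nadir and time to nadir of WBC, ANC and platelets are specified in the protocol, absent from the SAP text and not reported as dropped. The SAP's laboratory visit list leaves out 12 of 16 scheduled counts in Cycles 1 to 4, and off-schedule counts go to listings only, so the by-visit tables may understate how deep cytopenia goes.

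A reader might go further and conclude that the nadirs are lost, or that the trial's toxicity conclusions are compromised. Neither follows: every value stays in the by-patient listings with its grade, the adverse event tables carry most of the worst-grade information, and dose finding does not use these tables.

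The conclusion assumes that the test-schedule columns read as described, that 6.4 reflects the visits to be tabulated, and that the separate templates contain no nadir table. If 6.4 is only descriptive, the risk of understatement shrinks, but the missing nadir analysis remains.

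**What to change.** 1. **SAP 6.4:** add the Day 8, 15 and 22 blood counts of Cycles 1 to 4.
2. **SAP 8.7.6:** derive each patient's minimum WBC, ANC and platelets, and the time to each, from all post-baseline counts, scheduled or unscheduled. State the starting point of the clock, which Protocol 16.23 leaves open for nadirs. Summarise by renal group and dose level.
3. **Same table:** add worst laboratory CTCAE grade as a supplement to the adverse event tables, not a replacement.
4. **Unscheduled-visit rule:** keep it for by-visit summaries, with a stated exception for the nadir and worst-grade derivations.
5. **If the analysis is deliberately dropped:** declare and justify that in SAP 9.

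The cost is a few lines of SAP text and one derived table. The protocol already requires these counts. For the off-schedule ones, this assumes they are entered in the database, as their planned appearance in listings implies.
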